7 STATISTICAL METHODS & DETERMINATION OF SAMPLE SIZE

7.1 Statistical and Analytical Plans

The statistical methods provided in this protocol will be focused on primary and key secondary analyses. Complete and specific details of the statistical analysis will be described in the Statistical Analysis Plan (SAP).

The primary analysis will be performed after all ongoing, randomized subjects have completed at least 24 weeks of disease assessment or all subjects discontinue the study, whichever occurs first.

All statistical tests will be performed at two-sided significance level 0.05 unless otherwise specified.

7.2 Definition for Analysis Populations

The intent-to treat (ITT) population includes all randomized subjects in the study. Data from the ITT population will be analyzed by the treatment arm (Arm A: navitoclax + ruxolitinib, and Arm B: placebo + ruxolitinib) assigned at the time of randomization, regardless of the study drug treatment actually received. The ITT population will be used for analyses of all efficacy and baseline characteristics.

The safety population consists of all subjects who received at least 1 dose of study drug. The safety population will be used for all safety analyses.

7.3 Statistical Analyses for Efficacy

Primary Efficacy Analysis

Analysis of the primary endpoint SVR_{35W24} will be conducted by comparing the SVR_{35W24} rate (the proportion of subjects achieving SVR_{35} at Week 24), using the stratified Cochran-Mantel-Haenszel (CMH) test. The study is designed to test the null hypothesis:

H_0 : SVR_{35W24} rate in Arm A (navitoclax + ruxolitinib) = SVR_{35W24} rate in Arm B (placebo + ruxolitinib) against the alternative hypothesis H_1 : SVR_{35W24} rate in Arm A \neq SVR_{35W24} rate in Arm B.

The stratification factors for the stratified statistical analyses will be described in detail in the SAP.

The 95% confidence interval (CI) for SVR_{35W24} rate will be estimated for each treatment arm based on the exact binomial distribution. Subjects without spleen volume assessment at baseline or the Week 24 timepoint will be treated as non-responders. Details of this analysis will be provided in the SAP.

Secondary Efficacy Analyses

The following secondary endpoints will be analyzed:

- Response rate endpoints: SVR_{35} , anemia response, reduction in grade of bone marrow fibrosis from baseline as measured by the European consensus grading system
- Continuous endpoints: Change in TSS at Week 24 from baseline, as measured by MFSAF v4.0; change in fatigue at Week 24 from baseline, as measured by the PROMIS Fatigue SF 7a; change in physical functioning at Week 24 from baseline, as measured by EORTC QLQ-C30 v3.0
- Time to event endpoints: Duration of SVR_{35} , OS, and LFS

Change in TSS at Week 24 from baseline is defined as the change in total symptom score at Week 24 from baseline, as measured by MFSAF v4.0.

SVR_{35} rate is defined as the proportion of subjects who achieve at least 35% reduction in spleen volume from baseline (SVR_{35}) at any time during the study.

Duration of SVR_{35} is defined as time from the first achievement of SVR_{35} to the first assessment where the spleen volume is less than 35% reduction from baseline and is at least 25% increase from the nadir (the lowest spleen volume).

Change in fatigue at Week 24 from baseline is defined as the change in fatigue score at Week 24 from baseline, measured by PROMIS Cancer Fatigue SF 7a.

Change in physical functioning at Week 24 from baseline is defined as the change in physical functioning score at Week 24 from baseline, as measured by EORTC QLQ-C30.

Anemia response rate is defined as the proportion of subjects who achieve anemia response at any time during the study.

Overall survival is defined as time from randomization to death from any cause.

Leukemia-free survival is defined as time from randomization to leukemic transformation ($\geq 20\%$ blasts) by bone marrow blasts or peripheral blood blasts per IWG criteria, or death from any cause, whichever occurs earlier.

Rate of reduction in grade of bone marrow fibrosis is defined as the proportion of subjects who achieve reduction of at least 1 grade in bone marrow fibrosis measured by the European consensus grading system.

Unless otherwise specified, all response rate secondary endpoints will be analyzed using the stratified CMH test. The point estimate and 95% CIs based on the exact binomial distribution will be presented for each treatment arm. Unless otherwise specified, subjects with missing data for a visit will be treated as non-responders for that visit.

Unless otherwise specified, all time to event secondary endpoints will be analyzed by using stratified log-rank test. Subjects who do not experience the event of interest will be censored at the last adequate assessment. The hazard ratio (HR) for treatment effect and the corresponding 95% CI will be estimated using stratified Cox proportional hazards model. In addition, survivorship functions will be estimated by using Kaplan-Meier product-limit method. Estimated survival curves will be presented.

Unless otherwise specified, all continuous patient-reported outcome endpoints will be analyzed using the linear mixed effects model. Subjects with missing data will be handled by the missing at random assumption within the framework of the linear mixed effects model.

Statistical analyses of secondary endpoints will be described in detail in the SAP.

Additional Efficacy Analyses

Details of additional efficacy analyses will be provided in the SAP. Additional supportive efficacy statistical analyses may be performed if deemed necessary and helpful in understanding the drug effect.

Subgroup Analysis for Efficacy

Supportive subgroup analyses, such as platelet count and DIPSS+, will be performed for the primary endpoint. Details of subgroup analyses will be provided in the SAP.

7.4 Statistical Analyses for Safety

Safety analyses will be performed using the safety population.

Details of the safety analyses will be provided in the SAP.

7.5 Interim Analysis

There is no plan for any interim efficacy analysis. However, an IDMC will review unblinded safety data from the ongoing study (see Section 5.12). The primary responsibility of the IDMC will be to protect the safety of the subjects participating in this study and make the necessary recommendations.

7.6 Overall Type I Error Control

Overall type I error rate will be controlled for multiplicity for the primary and selected secondary efficacy endpoints. Hierarchical/sequential testing approach will be used to control the overall type I error rate at two-sided 0.05 significance level.

The key secondary efficacy endpoints are ranked as follows: 1. Change in TSS at Week 24 from baseline; 2. SVR₃₅; 3. Anemia response; 4. Reduction in grade of bone marrow fibrosis from baseline; 5. OS; 6. LFS; 7. Change in fatigue at Week 24 from baseline; 8. Change in physical functioning at Week 24 from baseline.

For endpoints to be analyzed more than once (such as OS and LFS), the Lan-DeMets alpha-spending function with O'Brien-Fleming boundary will be used to determine the efficacy boundaries for planned analyses. Additional details will be provided in SAP.

7.7 Sample Size Determination

Approximately 230 subjects will be enrolled using a 1:1 randomization ratio to Arm A and Arm B by the stratification factors (DIPSS+: intermediate-2 versus high risk, and platelet count: $\leq 200 \times 10^9/L$ versus $> 200 \times 10^9/L$). The null hypothesis H_0 will be tested against the alternative hypothesis H_1 using the stratified CMH test with two-sided significance level 0.05.

Based on published results, the SVR_{35W24} rate in the control arm (Arm B) is expected to be approximately 40%.¹⁵ True improvement in SVR_{35W24} from 40% to [REDACTED] is considered clinically meaningful.

This study with 230 subjects will have approximately 90% power if the true SVR_{35W24} rates in the control (placebo + ruxolitinib) and treatment (navitoclax + ruxolitinib) arms are 40% and [REDACTED], respectively.

With a total of 230 subjects, the study will also have approximately [REDACTED] power to detect a statistically significant OS improvement in the navitoclax + ruxolitinib treatment arm, assuming a true hazard ratio of [REDACTED]. A total of two OS analyses are planned: the first will be performed at the time of approximately 70% OS information (or [REDACTED] death events); the final OS Analysis will be performed when a total of [REDACTED] death events (100% OS information) have been observed. The Lan-DeMets alpha-spending function with O'Brien-Fleming boundary will be used to determine the efficacy boundaries for these planned OS analyses.

8 ETHICS

8.1 Independent Ethics Committee/Institutional Review Board (IEC/IRB)

The protocol, informed consent form(s), recruitment materials, and all subject materials will be submitted to the IEC/IRB for review and approval. Approval of both the protocol and the informed consent form(s) must be obtained before any subject is enrolled. Any amendment to the protocol will

require review and approval by the IEC/IRB before the changes are implemented to the study. In addition, all changes to the consent form(s) will be IEC/IRB approved.

8.2 Ethical Conduct of the Study

The study will be conducted in accordance with the protocol, Operations Manual, International Council for Harmonisation of Technical Requirements for Pharmaceuticals for Human Use (ICH) guidelines, applicable regulations, and guidelines governing clinical study conduct and the ethical principles that have their origin in the Declaration of Helsinki. Responsibilities of the investigator are specified in [Appendix B](#).

In the event a significant disaster/crisis (e.g., epidemic/pandemic, natural disaster, conflict/combat) occurs leading to difficulties in performing protocol-specified procedures, AbbVie may engage with study site personnel in efforts to ensure the safety of subjects, maintain protocol compliance, and minimize risks to the integrity of the study while trying to best manage subject continuity of care. This may include alternative methods for assessments (e.g., phone contacts or virtual site visits), alternative locations for data collection (e.g., use of a local lab instead of a central lab), and shipping investigational product and/or supplies direct to subjects to ensure continuity of treatment where allowed. In all cases, these alternative measures must be allowed by local regulations and permitted by IRB/IEC. Investigators should notify AbbVie if any urgent safety measures are taken to protect the subjects against any immediate hazard.

8.3 Subject Confidentiality

To protect subjects' confidentiality, all subjects and their associated samples will be assigned numerical study identifiers or "codes." No identifiable information will be provided to AbbVie.

9 SOURCE DOCUMENTS AND CASE REPORT FORM COMPLETION

The investigator is responsible for ensuring the accuracy, completeness, legibility, and timeliness of the data reported. All source documents should be attributable, legible, contemporaneous, original, accurate, and complete to ensure accurate interpretation of data. Clinical site monitoring is conducted to ensure that the rights and well-being of human subjects are protected, that the reported trial data are accurate, complete, and verifiable, and that the conduct of the trial is in compliance with the currently approved protocol, ICH Good Clinical Practice (GCP), and applicable local regulatory requirement(s) including the archiving of essential documents. During the COVID-19 pandemic, remote monitoring of data may be employed if allowed by the local regulatory authority, IRB/IEC, and the study site.

10 DATA QUALITY ASSURANCE

AbbVie will ensure that the clinical trial is conducted with a quality management system that will define quality tolerance limits in order to ensure human subject protection and reliability of study results. Data

will be generated, documented, and reported in compliance with the protocol, ICH GCP, and applicable regulatory requirements.

11 START AND COMPLETION OF THE STUDY

The start-of-study is defined as the date of the first site activated.

The end-of-study is defined as the date of the last subject's last visit or date of last follow-up contact with the subject, whichever is later, in the last country where the study was conducted.

APPENDIX A. STUDY SPECIFIC ABBREVIATIONS AND TERMS

Abbreviation	Definition
AE	Adverse event
Ag	antigen
ALT	Alanine aminotransferase
ANC	Absolute neutrophil count
aPTT	Activated partial thromboplastin time
AST	Aspartate aminotransferase
AUC ₀₋₁₂	Area under the curve from 0 to 12 hours
BCL-2	B-cell lymphoma-2
BCRP	Breast cancer resistance protein
BET	Bromodomain and extra-terminal motif
BH3	B-cell lymphoma 2 homology 3
BUN	Blood urea nitrogen
CI	Confidence interval
CL/F	Apparent oral clearance
CLL	Chronic lymphocytic leukemia
CMH	Cochran-Mantel-Haenszel
COVID-19	Coronavirus disease 2019
CSF	Colony stimulating factor
CT	Computed tomography
CTCAE	Common Terminology Criteria for Adverse Events
CYP	Cytochrome P450
DIPSS+	Dynamic International Prognostic Scoring System Plus
DNA	Deoxyribonucleic acid
DSUR	Development Safety Update Report
DTP	Direct-to-patient
EC ₅₀	Concentration required for 50% effect
ECG	Electrocardiogram
eCOA	Electronic clinical outcome assessments
ECOG	Eastern Cooperative Oncology Group
eCRF	Electronic case report form

EDC	Electronic data capture
ELN	European LeukemiaNet
EORTC	European Organisation for Research and Treatment of Cancer
EQ-5D-5L	EuroQol 5 Dimensions 5 Levels Health State Instrument
ESR	Erythrocyte sedimentation rate
FFPE	Formalin-fixed paraffin-embedded
FISH	Fluorescence In Situ Hybridization
FLT3	FMS-like tyrosine kinase 3
FSH	Follicle-stimulating hormone
GCP	Good Clinical Practice
GGT	Gamma-glutamyl transferase
Hb	Hemoglobin
HBV	Hepatitis B virus
HCG	Human chorionic gonadotropin
HCV	Hepatitis C virus
HIV	Human immunodeficiency virus
HMR	High molecular risk
HR	Hazard ratio
HRQoL	Health-related quality of life
HSCT	Hematopoietic stem cell transplantation
ICH	International Council for Harmonisation of Technical Requirements for Pharmaceuticals for Human Use
IDMC	Independent data monitoring committee
IEC	Independent ethics committee
IGRA	Interferon-gamma release assay
IMP	Investigational medicinal product
INR	International normalized ratio
Int	Intermediate
IRB	Institutional review board
IRT	Interactive response technology
ITT	Intent-to-treat
IUD	Intrauterine device
IUS	Intrauterine hormone-releasing system
IWG	International Working Group

JAK1	Janus kinase 1
JAK2	Janus kinase 2
LDL	Low-density lipoprotein
LFS	leukemia-free survival
LMWH	Low molecular weight heparin
MCL-1	Myeloid cell leukemia 1
MedDRA	Medical Dictionary for Regulatory Activities
MF	Myelofibrosis
MFSAF	Myelofibrosis Symptom Assessment Form
MRI	Magnetic resonance imaging
mRNA	messenger ribonucleic acid
NCI	National Cancer Institute
NRS	Numeric rating scale
NSAID	nonsteroidal anti-inflammatory drug
OS	Overall survival
PBMC	Peripheral blood mononuclear cell
PCP	Pneumocystis carinii pneumonia
PET	Post essential thrombocythemia
PFS	Progression-free survival
PGIC	Patient Global Impression of Change
PGIS	Patient Global Impression of Severity
P-gp	P-glycoprotein
PK	Pharmacokinetic
Plt	Platelet
PMF	Primary myelofibrosis
PPD	Purified protein derivative
PPV	Post polycythemia vera
PR	Partial remission
PRO	Patient-reported outcome
PROMIS	Patient-Reported Outcomes Measurement Information System
PT	Prothrombin time
Q12	Every 12 (weeks)
Q24	Every 24 (weeks)
QLQ	Quality of life questionnaire

QoL	Quality of life
QTc	QT interval corrected for heart rate
QTcF	QT interval corrected for heart rate using Fridericia's formula
RBC	Red blood cell
RNA	Ribonucleic acid
RPTD	Recommended Phase 2 dose
RSI	Reference Safety Information
SAE	Serious adverse event
SAP	Statistical analysis plan
SAR	Serious adverse reaction
SARS-CoV-2	Severe acute respiratory syndrome coronavirus 2
SDAC	Statistical data analysis center
SF	Short form
SMF	Secondary myelofibrosis
SmPC	Summary of product characteristics
SOC	System organ class
SSRI	Selective serotonin re-uptake inhibitors
SUSAR	Suspected unexpected serious adverse reaction
SVR ₃₅	At least 35% spleen volume reduction from baseline
SVR _{35W24}	At least 35% reduction in spleen volume at Week 24 from baseline
TA MD/SD	Therapeutic Area Medical Director/Scientific Director
TB	Tuberculosis
TCV	Treatment completion visit
TSS	Total symptom score
TSS _{50W24}	At least 50% reduction in total symptom score at Week 24 from baseline
ULN	Upper limit of normal
USA	United States of America
USPI	United States prescribing information
v	Version
VAS	Visual analogue scale
V/F	Apparent volume of distribution
WBC	White blood cell
WHO	World Health Organization

APPENDIX D. ACTIVITY SCHEDULE

The following table shows the required activities. The individual activities are described in detail in the **Operations Manual**.

Study Activities Table

Activity	Screening/ Baseline	Week 1	Week 1	Week 2	Week 3	Week 5	Week 7	Week 9	Week 13, 17, 21, 25	Q12 weeks as of Week 37	Treatment Completion Visit	30-Day Safety Visit (± 3 Days)	Post-Treatment Visits (± 3 Weeks)	Survival Follow Up
	Day -28 to Day -1	Day 1	Day 2	Day 1 (± 1 day)	Week 13, 17, 21 Day 1 (± 2 days). Week 25 Day 1 (± 3 days)	From Week 37 Day 1 (± 4 days)								
INTERVIEWS & QUESTIONNAIRES														
Informed consent	✓													
Eligibility criteria	✓													
Medical/surgical/transfusion history	✓	✓												
Alcohol and nicotine use	✓													
Adverse event assessment	✓	✓	✓	✓	✓	✓	✓	✓	✓	✓	✓	✓		
Prior/concomitant therapy/transfusion	✓	✓	✓	✓	✓	✓	✓	✓	✓	✓	✓			
Post-treatment therapy/transfusion/surgery												✓	✓	✓
MFSAF v4.0 (Daily)	✓	✓ (Daily through end of Week 36)												
EORTC QLQ-C30 v3.0		✓				✓			✓ (Week 13, 25)	✓	✓			
PROMIS Fatigue SF 7a	✓	✓				✓			✓ (Week 13, 25)	✓	✓			
EQ-5D-5L		✓				✓			✓ (Week 13, 25)	✓	✓			
PGIC									✓ (Week 13, 25)					

Activity	Screening/ Baseline	Week 1	Week 1	Week 2	Week 3	Week 5	Week 7	Week 9	Week 13, 17, 21, 25	Q12 weeks as of Week 37	Treatment Completion Visit	30-Day Safety Visit (± 3 Days)	Post-Treatment Visits (± 3 Weeks)	Survival Follow Up
	Day -28 to Day -1	Day 1	Day 2	Day 1 (± 1 day)	Week 13, 17, 21 Day 1 (± 2 days). Week 25 Day 1 (± 3 days)	From Week 37 Day 1 (± 4 days)								
PGIS	✓	✓							✓ (Week 13, 25)					
ECOG performance status	✓	✓		✓	✓	✓	✓	✓	✓	✓	✓			
Survival follow-up call (approximately every 2 months for up to 8 years)														✓
LOCAL LABS & EXAMS														
MRI (or CT scan) for spleen assessment	✓								✓ (Week 13, 25)	✓ (Week 37, 49, 73, 97)	✓		✓	
12-lead ECG	✓					✓					✓			
Vital signs: including height (Screening only), weight, BP, pulse, and body temperature	✓	✓		✓	✓	✓	✓	✓	✓	✓	✓	✓		
Physical examination including skin examination, spleen and liver measurement by palpation	✓	✓		✓	✓	✓	✓	✓	✓	✓	✓		✓	
Disease Assessment by IWG									✓ (Week 13, 25)	✓ (Week 37, 49, 73, 97)	✓		✓	
Serum/urine pregnancy test	✓	✓				✓		✓	✓ (monthly from Week 25 where a	✓ (monthly where a regulatory requirement)	✓			

Activity	Screening/ Baseline	Week 1	Week 1	Week 2	Week 3	Week 5	Week 7	Week 9	Week 13, 17, 21, 25	Q12 weeks as of Week 37	Treatment Completion Visit	30-Day Safety Visit (± 3 Days)	Post-Treatment Visits (± 3 Weeks)	Survival Follow Up
	Day -28 to Day -1	Day 1	Day 2	Day 1 (± 1 day)	Week 13, 17, 21 Day 1 (± 2 days). Week 25 Day 1 (± 3 days)	From Week 37 Day 1 (± 4 days)								
									regulatory requirement)					
TB screening (PPD or IGRA)	✓													
Clinical chemistry, hematology, coagulation	✓	✓	✓ (hem only)	✓	✓	✓	✓	✓	✓	✓	✓		✓ (hem only)	
Lipid parameters – fasting state	✓								✓ (Week 13)					
Bone marrow biopsy and cytogenetic assessment (Screening plus standard of care) for local evaluation of disease	✓								✓ (Week 25)	✓ (Week 49, 73)	✓		✓	
Bone marrow aspirate for local evaluation of disease	✓								✓ (Week 25)	✓ (Week 49, 73)	✓		✓	
 CENTRAL LAB														
Blood samples for PK assay		✓		✓	✓	✓								
Blood for mutational profiling	✓								✓ (Week 13, 25)	✓ (Week 49, 73)	✓			
Blood for immune cell biology		✓							✓ (Week 25)	✓ (Week 49)				
Blood for PBMC		✓							✓ (Week 25)	✓ (Week 49)				

Activity	Screening/ Baseline	Week 1	Week 1	Week 2	Week 3	Week 5	Week 7	Week 9	Week 13, 17, 21, 25	Q12 weeks as of Week 37	Treatment Completion Visit	30-Day Safety Visit (± 3 Days)	Post-Treatment Visits (± 3 Weeks)	Survival Follow Up
	Day -28 to Day -1	Day 1	Day 2	Day 1 (± 1 day)	Week 13, 17, 21 Day 1 (± 2 days). Week 25 Day 1 (± 3 days)	From Week 37 Day 1 (± 4 days)								
Blood for plasma markers	✓								✓ (Week 13, 25)	✓ (Week 49)	✓			
Blood for allelic burden	✓								✓ (Week 13, 25)	✓ (Week 49, 73)	✓			
Blood for translational research	✓								✓ (Week 13, 25)	✓ (Week 49, 73)	✓			
Bone marrow biopsy (fibrosis grading/biomarker research)	✓								✓ (Week 25)	✓ (Week 49, 73)	✓		✓	
Bone marrow aspirate for mutational profiling	✓								✓ (Week 25)	✓ (Week 49, 73)	✓			
Bone marrow aspirate for allelic burden	✓								✓ (Week 25)	✓ (Week 49, 73)	✓			
Bone marrow aspirate for translational research	✓								✓ (Week 25)	✓ (Week 49, 73)	✓			
Optional Biomarker Sample: Whole Blood DNA and RNA		✓							✓ (Week 13)		✓			

Activity	Screening/ Baseline	Week 1	Week 1	Week 2	Week 3	Week 5	Week 7	Week 9	Week 13, 17, 21, 25	Q12 weeks as of Week 37	Treatment Completion Visit	30-Day Safety Visit (± 3 Days)	Post-Treatment Visits (± 3 Weeks)	Survival Follow Up
	Day -28 to Day -1	Day 1	Day 2	Day 1 (± 1 day)	Week 13, 17, 21 Day 1 (± 2 days). Week 25 Day 1 (± 3 days)	From Week 37 Day 1 (± 4 days)								
Rx TREATMENT														
Randomization/drug assignment		✓												
Dispense study drug; dispense subject dosing diary (Week 1 Day 1)		✓		✓	✓	✓	✓	✓	✓	✓	✓			
Review and copy subject dosing diary (Week 1 Day 1 to Week 5 Day 1) and perform drug reconciliation				✓	✓	✓	✓	✓	✓	✓	✓	✓		

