[figure not shown]
Treatment with study drugs may continue until end of clinical benefit or occurrence of unacceptable toxicity or discontinuation criteria have been met. At the end of study drug treatment, a treatment completion and 30-day safety visit will be conducted.

After documented disease progression or initiation of post-treatment cancer therapy, the subject will enter the survival follow-up phase.

The schematic of the study is shown in [Figure 1](#). Further details regarding study procedures are located in the Operations Manual.

See [Section 5](#) for information regarding eligibility criteria.

Figure 1. Study Schema

DIPSS+ = Dynamic International Prognostic Scoring System Plus; Int = intermediate; Plt = platelet; PMF = primary myelofibrosis; SMF = secondary myelofibrosis

Option for Safety Lead-In Phase

The Sponsor plans to review safety data from at least 6 subjects administered navitoclax in combination with ruxolitinib for at least 8 weeks in either the frontline cohort of Study M16-109 or Study M16-191. If the review of safety data from Study M16-109 is not completed prior to dosing the 12th subject in Study M16-191, enrolment will be paused to complete independent data monitoring committee (IDMC) review of safety data from the first 12 subjects enrolled in Study M16-191.

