Subjects with disease progression or relapse may continue to receive study treatment if the investigator considers it to be in the best interest of the subject. Disease assessment per protocol criteria at the time of disease progression will be captured in EDC. The subject will be monitored per study procedures described in [Appendix D](#). Activity Schedule or more often if the investigator considers it necessary.

For subjects to be considered lost to follow-up, reasonable attempts must be made to obtain information on the subject's final status. At a minimum, 2 telephone calls must be made and 1 certified letter must be sent and documented in the subject's source documentation.

AbbVie may terminate this study prematurely, either in its entirety or at any site. This study will be monitored regularly by AbbVie in addition to an independent data monitoring committee (IDMC). The study has a safety review plan to assess laboratory and adverse event data on a weekly basis and serious adverse events on a daily basis. An aggregate review of the blinded aggregated data will be conducted once every 3 months. The product safety team including cross functional members is responsible for the ongoing safety monitoring of the program, including recommendations to modify or discontinue the study for unanticipated safety events. The study may be terminated due to unfavorable risk benefit assessment or at the IDMC's recommendation based on safety or efficacy concerns. The investigator may also stop the study at his/her site if he/she has safety concerns. If AbbVie terminates the study for safety reasons, AbbVie will promptly notify the investigator; the investigator must promptly notify any subjects enrolled in the study and arrange alternative therapy for MF.

COVID-19 Pandemic-Related Acceptable Protocol Modification

During the COVID-19 pandemic, it has been necessary to employ mitigation strategies to enable the investigator to ensure subject safety and continuity of care. Acceptable mitigation strategies are identified and included in the Operations Manual ([Appendix I](#)).

The investigator should contact the AbbVie TA MD/SD before discontinuing a subject from the study for a reason other than "planned per protocol" to ensure that all acceptable mitigation steps have been explored.

Refer to the Operations Manual ([Appendix I](#)) for details of how to handle activities/procedures.

Interruption/Discontinuation of Study Drug Due to COVID-19 Infection

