5.7 Post-Treatment Follow Up

All subjects who discontinue study drug treatment after 24 weeks for reasons other than disease progression will return for post-treatment follow-up visits approximately every 12 weeks following the treatment completion visit to assess disease status until documented disease progression or leukemic transformation or initiation of post-treatment cancer therapy.

For subjects who discontinue study treatment prior to completing 24 weeks of study treatment without intervening new treatment for myelofibrosis and who do not have documented disease progression, disease response assessments, including MRI/CT scans, should be conducted per the visit schedule up to and including the Week 25 Day 1 visit. Once the Week 25 Day 1 disease response assessments are completed the subject will continue on study every 12 weeks in post-treatment follow up, or every 2 months in survival follow up, based on post-treatment status (i.e., subjects who achieve disease progression, have lost clinical benefit, or have started another treatment would move onto survival follow up).

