8.5.4 Progression-Free Survival (PFS)

Progression-free survival is defined as the time from randomization to the date of confirmed relapse or progressive disease, or death from any cause, whichever occurs earlier, on or prior to the start of post-study treatment. Subjects without any defined PFS event will be censored at the date of last adequate disease assessment on or prior to the start of post-study treatment. Subjects who are alive and without any adequate disease assessment will be censored at the date of randomization.

Progression-free survival will be analyzed using the statistical method described for time-to-event variables in Section 8.1.

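### Scheduled on-drug IWG assessments end at Week 97, so at late cutoffs the PFS curve is too low and the hazard ratio depends on how often each arm stops drug

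*Protocol*

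**What the plan says.** **On drug.** Protocol Appendix D labels the later on-treatment visits "Q12 weeks as of Week 37" and gives no last visit. Protocol 4.1 says: "Treatment with study drugs may continue until end of clinical benefit or occurrence of unacceptable toxicity or discontinuation criteria have been met". In that visit column the row "Disease Assessment by IWG" is restricted to "Week 37, 49, 73, 97", and the MRI/CT row carries the same restriction. Palpation, hematology and ECOG status are unrestricted in the same column, so the limit is particular to disease assessment and imaging. Both limited rows are ticked again at the treatment completion visit and at post-treatment visits.

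**Off drug.** Under Protocol 5.7, subjects who stop after 24 weeks without progression return "approximately every 12 weeks following the treatment completion visit to assess disease status until documented disease progression". Leukemic transformation or new cancer therapy also ends these visits.

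**Analysis.** SAP 8.5.4 counts confirmed relapse or progression, and death from any cause, up to the start of post-study treatment. It then says: "Subjects without any defined PFS event will be censored at the date of last adequate disease assessment", again no later than post-study treatment. SAP 8.1 accepts a single progressive response as confirmed if it is the subject's last. For subjects who progress and may stay on treatment, Protocol 5.5 says: "Disease assessment per protocol criteria at the time of disease progression will be captured in EDC". PFS is an exploratory endpoint (Protocol 3.3). It is analysed by stratified log-rank test, stratified Cox model and Kaplan-Meier, and it is not in the testing sequence of SAP 12.0, Table 1.

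**The concern.** After Week 97 the plan records failures when they happen but schedules no record that a subject still on drug remains free of progression. Whether a subject supplies PFS time beyond Week 97 then depends on having failed or stopped drug by the cutoff. That is informative censoring, not just sparse follow-up.

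Two things are at stake at a late cutoff. The Kaplan-Meier curve drops too fast in both arms, because the subjects doing best on treatment are removed. And if the arms differ in how often subjects stop for reasons other than progression, the removal is unequal, so the log-rank test and HR can differ from the null when true PFS is identical. Late cutoffs are foreseeable: the two OS analyses are event-driven and survival follow-up runs for up to 8 years.

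**Working it through.** The documents give no PFS event count, hazard, power or analysis date, so there is no plan figure to reproduce. All rates below are assumptions.

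**1. From schedule to censoring date, at a cutoff well past Week 97**

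| Subject's status | PFS time ends |
|---|---|
| On drug, no event | About Week 97, however long the follow-up |
| Progressed on drug after Week 97 | At progression, recorded when it occurs or at treatment completion |
| Died | At death |
| Stopped drug without progression | At treatment completion or the last 12-weekly visit after it |

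Under the scheduled visits, everyone who supplies time after Week 97 has progressed, died or stopped drug by the cutoff.

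**2. Why stop rates matter: a closed-form case**

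Assume 115 per arm (230 subjects, 1:1) and, in both arms, progression 0.003 and death 0.0015 per week, so an event hazard of 0.0045. Non-progression stops occur at 0.006 per week in one arm and 0.003 in the other. Accrual takes 100 weeks and the cutoff is week 240, so follow-up is uniform on 140-240 weeks. Every on-drug progression is recorded, and new therapy starts at once after a stop. Week 97 Day 1 is 96 weeks after Day 1.

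| Quantity | More stops | Fewer stops |
|---|---|---|
| Total exit rate per week | 0.0045 + 0.006 = 0.0105 | 0.0045 + 0.003 = 0.0075 |
| On drug, event-free at 96 weeks | 115 × e^(−1.008) = 42.0 | 115 × e^(−0.72) = 56.0 |
| Still so at cutoff, hence censored at about Week 97 | 115 × (e^(−1.47) − e^(−2.52))/1.05 = 16.4 | 115 × (e^(−1.05) − e^(−1.80))/0.75 = 28.3 |
| Supply time after Week 97 | 42.0 − 16.4 = 25.6 | 56.0 − 28.3 = 27.7 |
| Share of these with an event | 0.0045/0.0105 = 0.43 | 0.0045/0.0075 = 0.60 |
| Events as a share of all at risk at Week 97 | (0.43 × 25.6)/42.0 = 0.26 | (0.60 × 27.7)/56.0 = 0.30 |

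Both arms have the same hazard, and the true event shares are close (0.26 v 0.30; the gap reflects shorter time at risk with more stops). Among the subjects left in the risk set the shares are 0.43 v 0.60.

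A simulation of 60,000 subjects at these rates agrees: 16.1 and 28.5 censored at about Week 97, 25.7 and 27.3 supplying later time, event shares 0.43 and 0.60. The HR after Week 97 is 0.79 (true 1.02), and over the whole period 0.93 (true 1.01). Kaplan-Meier PFS at Week 144 is 0.416 and 0.371, against a true e^(−0.0045 × 144) = 0.523.

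Varying how fast new therapy starts and how many on-drug progressions are recorded, with no true difference, gives a late HR of 0.74-0.84 and a whole-period HR of 0.90-1.00. With equal stopping (0.004 in both arms) the late HR is 1.03, but Week 144 PFS is 0.444 and 0.449 against about 0.52.

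**3. Size of the test error**

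Assumed: 115 per arm, identical exponential PFS with median 208 weeks, follow-up 160-240 weeks, SAP 8.5.4 censoring.

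| Median time to non-progression stop | No new therapy after stopping | New therapy soon after stopping |
|---|---|---|
| 100 v 200 weeks | HR 0.88, rejection 10-12% | HR 0.91-0.92, rejection about 7% (6-8% across runs) |
| 100 v 400 weeks | HR 0.74-0.76, rejection 30-34% | HR 0.83-0.84, rejection 11-12% |

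Ranges span repeated runs. The right-hand column applies the rule that assessments and PFS end at new therapy (Protocol 5.7, SAP 8.5.4). With no new therapy, a milder contrast of 150 v 200 weeks gives HR 0.945 and 6%, and equal stopping gives 0.995 and about 5%.

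**4. Earlier cutoffs**

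With 100 weeks of accrual (assumed) and new therapy at a median of 12 weeks after stopping, the Week 24 cutoff (follow-up 24-124 weeks) gives HR 0.98-1.00 and about 5% rejection. The Week 48 cutoff (48-148 weeks) gives HR 0.95-0.97 and 4-7%.

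**5. Higher progression hazard off drug**

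If that hazard is 2-3 times higher, the true late HR is 1.11-1.24 and the rule gives 0.79-0.94. In extreme cases (5-fold, few deaths, on-drug progression undetected) the true late HR is 1.33-2.01 and the rule gives 0.99-1.05.

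**The case against.** The strongest reply concerns reach. PFS is exploratory and outside the ranked hierarchy, so no primary or key secondary result and no allocated alpha is touched. SAP Table 1 schedules no PFS test at the OS analyses. At the Week 24 and Week 48 cutoffs the effect is small. All of this stands, and it limits the severity.

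A reader might infer that the plan will make navitoclax look better on PFS, with a false-positive rate near 30%. The documents do not support that:

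- They give no stop rates by arm. Thrombocytopenia is named as navitoclax's primary dose-limiting toxicity, and 83% of Study M16-109 subjects had a navitoclax dose reduction, but a dose reduction is not a stop. Unequal stopping is plausible, not shown.
- The 30-34% figures need a 100 v 400 week contrast and no new therapy after stopping. Protocol 2.1 says that patients who stop ruxolitinib rapidly become symptomatic, so early new therapy is credible, and the rate is then 11-12%.
- With a much higher off-drug hazard, the arm with more stops looks less bad rather than better.

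Some details are also unseen. The Operations Manual is not in the text provided, the SAP does not define an adequate assessment, and Protocol 5.5 allows monitoring more often at the investigator's discretion. Discretionary assessments could soften the effect, but they do not restore equal ascertainment.

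**Conclusion.** The concern holds in a bounded form. Following the schedule and SAP 8.5.4 together biases PFS after Week 97. At cutoffs well past that visit, Kaplan-Meier PFS is too low in both arms even with equal stopping. With unequal non-progression stopping, the comparison shifts toward the arm with more stops: HR about 0.88-0.92 with 7-12% rejection (100 v 200 weeks), and about 0.74-0.84 with 11-34% (100 v 400 weeks). The direction was the same in every unequal-stopping scenario examined. The size rests on assumed stop, progression, death and new-therapy rates and on 160-240 weeks of follow-up. Because PFS is exploratory, this is a minor-to-moderate issue with a cheap remedy.

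**What to change.** In SAP 8.5.4, for any cutoff at which subjects are past Week 97, base the between-arm PFS comparison on data up to the Week 97 visit plus its 4-day window. Count events to that point and censor event-free subjects at their last adequate assessment on or before it. Report the full-follow-up PFS analysis as supplementary, with a note that assessment after Week 97 differs between subjects on and off drug. In the section 3 simulation setting, ending the comparison at Week 97 gave HR 0.98-1.02 and 4-6% rejection.

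The cost is SAP wording. The downside is that PFS events after Week 97, deaths included, leave the main comparison, though they are still reported. A smaller inequality remains before Week 97, because scheduled on-drug assessments are 24 weeks apart between Weeks 49 and 97.

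Completing the IWG form at the existing on-drug visits after Week 97 would be a weaker remedy. It changes the protocol schedule and would not fully equalise assessment, since on-drug MRI/CT ends at Week 97 and marrow at Week 73 while post-treatment visits include both.
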